3.8 Allowed Concomitant Medications and Prohibited Treatments

Only acetaminophen is permitted for pain while in the study. NSAIDS and other non-acetaminophen pain medication are not permitted for the first 6 months of the study. Oral steroids, steroid injections and Viscosupplementation injections are not permitted for the first 6 months (180 days) of the study.

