3.1 Study Design

This study is primarily investigating the effectiveness ACP IA in patients with OA of the knee in reducing pain.

This study is a prospective, multicenter, double blind, clinical study with up to 5 sites, approximately 90 subjects who are candidates for IA ACP treatments for knee OA. Ninety (90) subjects will be randomized to receive three single weekly intraarticular (IA) injection of either ACP (n=60) or Phosphate buffered saline (n=30).

To evaluate the effectiveness of three weekly doses IA of 3-6 ml of ACP injected into the knee from baseline through 6 months (180 days).

All patients will have a screening visit and three treatment visits one week apart (Visit 2 / Week 0, Visit 3 / Week 1, and Visit 4/ Week 2), followed by three follow-up visits; Visit 5/ 2 months (60 days) Visit 6/ 3 months (90 days) and Visit 7/ 6 month (180 days) after the 1st treatment visit.

Patients will have an additional follow-up Study visit at Visit 8/12 month (365 days) after the 1st treatment visit. Note: Once the **last patient** has reached their 6 month Visit (180 days), an analysis of the co-primary endpoints will be performed based on 6-month (180 days) outcomes. Subjects will remain blinded to treatment throughout the study.

3.2 Study Hypotheses and Endpoints3.2.1 Primary Effectiveness Hypotheses for Pain:

ACP treatment is superior to control in terms of mean change from baseline to 6 month (180 days) in the WOMAC Pain score.

3.2.2 Conditional Effectiveness Hypotheses for Function:

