6.2.1 Screening Visit 1 (-7 to -2 days)

Once the subject has signed the informed consent and prior to treatment, he/she will have the following data collected and procedures conducted:

- Medical history/Demographics
- Physical exam (Temperature, heart rate and blood pressure)
- Radiograph(s) (if not part of medical record) refer to section 6.1.1
- Urine pregnancy test (for females with childbearing potential)
- Concomitant Analgesics/Treatment review
- WOMAC survey (pain, stiffness, function)
- Inclusion/exclusion criteria review
- Kellgren-Lawrence grading
- Strokes Test Grading

• Inform subjects that they will return for visit 2 to receive their 1st IA injection and then to return at 1 week and 2 weeks for an additional IA injection. Additionally, inform that they will need to return for visits at 2, 3 and 6 months post-treatment 1st injection.

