6.3 Study Visits

6.3.1 Treatment Visits

All subjects enrolled in the study will have the following procedures at visit 3 (1 week +/- 3 days) & visit 4 (2 weeks +/- 3 days):

- WOMAC survey (pain, stiffness, function)
- Concomitant Analgesics/Treatment review
- Adverse event assessment /device complications as defined in Section 7
- Venipuncture, processing, blinding and IA procedure.
- Refer to Visit 3 and 4 Venipuncture and Blood Collection Procedure (Appendix 2-3)
- Refer to Blinding Procedure (Appendix 2-5)

• Refer to Visit 2, 3 and 4 Intra-Articular Injection (Appendix 2-4)

6.3.2 Follow-Up Visit 5 [2 months (60 days)+/- 7 days], Visit 6 [3 months (90 days)+/- 7 days] & Visit 7 [6 months (180 days) +/- 14 days]

- WOMAC survey (pain, stiffness, function)
- Concomitant Analgesics/Treatment review
- Adverse event assessment

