8.3 Statistical Methods for Testing Superiority

8.3.1 MMRM

Superiority testing will be performed using a mixed model for repeated measures (MMRM) analysis of covariance (ANCOVA) Model.³⁹ The MMRM approach is a direct likelihood approach requiring specialized statistical software. For this study, all MMRM parameters will be estimated using SAS PROC MIXED. The MMRM model is notable for its inclusion of all available data from all eligible subjects and does not require their exclusion as in complete case analysis or arbitrary assignment of some value as in Last Observation Carried Forward (LOCF). Inclusion of outcome data from time points earlier than Months 6 informs the implicit imputation of missing Month 6 values through the covariance matric used to model the random effects.

The random effects in the MMRM model will based on the so-called 'unstructured covariance matrix' in which variances over time are allowed to vary as are the pair-wise correlations over time.

The values over time will include all WOMAC scores, namely at each of the 3 follow-up time points, visit 5 / 2 months, visit 6 / 3 months, and visit 7 / 6 months.

All WOMAC values will be included in the analysis even if they are obtained outof-window. However, the fraction of out-of-window visits will be summarized at each time point.

The contrast indicated by the primary hypotheses above, $\delta(pain)_{ACP} - \delta(pain)_{Control}$ will be estimated as the treatment group contrast from baseline to Month 6 in the WOMAC score derived from the MMRM. The null hypothesis is that the true value of this contrast is equal to zero. The same approach will be taken for the WOMAC Function score if superiority in pain relief is demonstrated.

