Appendix 2-1 Schedule of Events

	Screening	Т	reatment Vis	its		Follow	v —up Visits	
ACP IA FOR KNEE OA	Visit 1	Visit 2	Visit 3	Visit 4	Visit 5	Visit 6	Visit 7	Visit 8
	Day -2 to 07	Day 0	Week 1 +/- 3 days	Week 2 +/- 3 days	2 months +/- 7 days	3 months +/- 7 days	6 months +/- 14 days	EOS or 1year +/- 30 days
Informed Consent	X ¹							
History & Demographics	X ²							
Physical Exam (VS) • Knee Exam • Kellgren-Lawrence Grading • Strokes Test Grading	X ³							
Concomitant Medication/Therapy	X4	X 4	X ⁴	K 4	X4	X 4	X⁴	X4
WOMAC	X ⁵		X⁵	K₂	X ⁵	K₂	X₂	X ⁵
Enrollment Pregnancy (urine) Radiograph	X6	X 6						
Randomization		x						
Visit	X7	X 7	X 7	K 7	X 7	K 7	X 7	X ⁷
Treatment		X ⁸	X ⁸	K ⁸				
AE		X 9	X 9	Х ⁹	X ⁹	X 9	X9	X۹
Deviation	X ¹⁰	X ¹⁰	X ¹⁰	X ¹⁰	X ¹⁰	X ¹⁰	X ¹⁰	X ¹⁰
Completion								X ¹¹
Heme Profile		X ¹²						

Informed Consent process is conducted and the form is signed prior to any study related procedures.
 Medical & Surgical History and Demographics are collected at Screening
 Physical Exam (including Knee exam, Kellgren-Lawrence & Strokes Test) is done at screening
 Pain medication and therapy review are collected at screening and reviewed at each study visit
 WOMAC is completed at screening visit to confirm Inclusion Criteria # 4
 Available Inclusion/Exclusion Criteria is collected at screening and confirmed at V2 (Day 0) prior to randomization. Radiographs to confirm Inclusion #3 and exclusion #1 and 3. Radiographs are done prior to Randomization, if not complete and part of subject's medical historical medical record. Urine pregnancy is done at screening as when applicable.
 Visit Data collected all study Visits.
 Treatment form is collected at V2, V3 & V4.
 Adverse Events are collected at applicable at V2 thru V8.
 Deviations are collected at each V1 thru V8.
 Study Completion is done at Visit 8 or sooner if discontinues prior to Visit 8.

12. Whole blood and ACP collected for analysis.

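### Section 3.8, read literally, lifts the bar on steroids and viscosupplementation at Day 180, while the primary Month 6 WOMAC may be taken up to Day 194; tying the bar to that score is a cheap improvement

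*Combined protocol and SAP*

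**What the plan says.** **Restrictions.** Section 3.8 has three sentences on treatment.

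- The first is open-ended: "Only acetaminophen is permitted for pain while in the study".
- The second limits other analgesics by time: "NSAIDS and other non-acetaminophen pain medication are not permitted for the first 6 months of the study".
- The third gives a day count: "Oral steroids, steroid injections and Viscosupplementation injections are not permitted for the first 6 months (180 days) of the study".

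**Timing of the primary score.** Section 3.1 counts follow-up from the first injection: "Visit 7/ 6 month (180 days) after the 1st treatment visit". Section 6.3.2 gives the window: "Visit 7 [6 months (180 days) +/- 14 days". The Schedule of Events (Appendix 2-1) agrees: "6 months +/- 14 days".

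**Analysis.** Section 8.3.1 does not discard late scores: "All WOMAC values will be included in the analysis even if they are obtained" out of window. Section 8.8.1 places the primary analysis in the mITT set and removes patients with confounding medication only from the per-protocol set.

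No sentence in the document links the end of the restrictions to completion of the Visit 7 WOMAC.

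**The concern.** The restriction is written as a fixed length of time, and the primary assessment as a window that extends past it. A site following 3.8 to the letter could allow a steroid or hyaluronic acid injection on, say, Day 183 and collect the primary score on Day 190. That treatment might not even be logged as a deviation.

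The score is open to such treatment. The WOMAC form in Appendix 2-6 asks about the last 48 hours. Section 2.2 reports that hyaluronic acid differed from placebo in pain at 1 to 4 weeks, and that corticosteroids relieved pain more than hyaluronic acid at 0 to 4 weeks. A score taken 1 to 14 days after an injection could therefore reflect it.

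More use in the control arm would shrink the ACP-control difference. More use in the ACP arm would enlarge it. Equal use would leave it about unchanged.

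**Working it through.** **1. Size of the gap.**

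- Visit 7 window: 180 − 14 = Day 166 to 180 + 14 = Day 194, which is 29 days (Sections 3.1 and 6.3.2).
- Literal end of the bar, counted from first treatment as follow-up is: Day 180.
- Window days after the bar: Days 181 to 194 = 14. Share: 14/29 = 48%.

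This is a share of calendar days, not a forecast of when visits happen.

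**2. The plan's own power figure.** Section 8.4.1 uses a two-sample t-test, one-sided α = 0.025, standardized difference 0.80, 2:1 allocation, 90% power, N = 78 (52/26). Power from the noncentral t distribution has df = n₁ + n₂ − 2 and noncentrality d/√(1/n₁ + 1/n₂):

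- 50/25: 89.7%
- 52/26: 90.8%
- 60/30: 94.3%

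So 78 is the smallest 2:1 total that reaches 90%, and the plan's figure is reproduced. Nothing in this point changes N, α or the stated power.

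**3. How much contamination would matter.** With the plan's SD of 3.4, the planned difference is 0.80 × 3.4 = 2.72 points. If a fraction *f* more of the controls than of the ACP patients receives a treatment worth *k* points, the difference falls by *f* × *k*. To bring power down to 80%:

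| | 52/26 | 60/30 |
|---|---|---|
| Standardized difference giving 80% power | 0.682 | 0.633 |
| In points (× 3.4) | 2.317 | 2.154 |
| Loss from 2.72 | 0.403 | 0.566 |
| Net control excess needed, *k* = 3 | 0.403/3 = 13.4% | 0.566/3 = 18.9% |
| Net control excess needed, *k* = 2 | 0.403/2 = 20.1% | 0.566/2 = 28.3% |

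The values of *k* are assumptions; the documents give neither an effect on WOMAC Pain nor a rate of use.

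Only patients seen after Day 180 can be affected within the window. If visits were spread evenly (assumption), 48% would be late. With no use in ACP, the share of late-seen controls needing treatment within at most 14 days would be 13.4/0.483 = 28% to 20.1/0.483 = 42% at 52/26, and 39% to 59% at 60/30.

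If the true difference were the 4.2 points that 8.4.1 calls conservative, the loss needed would be 4.2 − 2.317 = 1.88 or 4.2 − 2.154 = 2.05 points.

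**4. Smaller scenarios at 52/26, use in controls only (assumption).** 5% treated with a 2-point effect gives 88.6% power; 10% with 2 points gives 86.1%; 10% with 4 points gives 80.1%.

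**The case against.** **The label.** The phrase pairing six months with 180 days is the protocol's standing name for the Month 6 time point, including in the endpoint definition in 3.2.3. It is inconsistent to give that label a two-week window for the WOMAC and read it as a hard stop in 3.8. This stands as a plausible reading of intent, and is why the text is called ambiguous. It does not settle the matter: 3.8 states a duration, and two sites could apply it differently in good faith.

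**The acetaminophen sentence.** It could cover a knee injection given for pain at any time in the study. That also stands in part. But it does not name these treatments or reach an oral steroid taken for another illness, and it fits poorly with the sentences after it: if it barred every other pain treatment throughout, the six-month limit on NSAIDs would serve no purpose.

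**Existing safeguards.** Concomitant treatment is recorded at each visit (8.6), the visit form asks about additional therapy and injections (Appendix 2-6), and concomitant medications are among the critical data with full source verification (9.10). The per-protocol set drops confounded patients. These make contamination visible and support a sensitivity analysis; they do not keep it out of the primary mITT result. Nor would clearer wording do so fully, since patients who break the rule stay in mITT. It would only make such use less likely.

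**Stronger readings to avoid.** A reader might count the 180 days from screening ("Screening Visit 1 (-7 to -2 days") and so enlarge the gap. The documents do not support this: Sections 3.1 and 6.2 count follow-up from the first injection, and nothing counts 180 days from screening. A reader might also infer that the primary result will be biased or the type 1 error inflated. No usage rate is given, the arms are blinded, and equally effective arms should have similar use, so neither is shown.

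**Conclusion.** The point holds as a cheap improvement. Read literally, 3.8 ends the bar at Day 180, the primary score may be taken up to Day 194, and patients treated in between remain in the primary analysis. The wording may have been meant to run to the Month 6 visit, but it does not say so.

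The direction of any bias cannot be found from the documents. Its size is probably small: a material loss of power needs a net control excess of roughly 13 to 28 percentage points of patients, under an assumed effect of 2 to 3 points, the plan's SD of 3.4 and a true difference of 2.72 points. If the true difference is nearer 4.2 points, far more would be needed. The case for the change rests on its low cost and on removing an ambiguity just before the score that decides the trial.

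**What to change.** Add one sentence to 3.8: *all restrictions in this section, including those on NSAIDs and other analgesics, apply from the first treatment at the latest until the Visit 7 (Month 6) WOMAC is completed or, if Visit 7 does not take place, until the visit window closes at Day 194.*

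This closes the in-window gap, gives the analgesic and injection restrictions the same end point, and gives patients who do not return a definite end date. No sample size, α, visit or model changes.

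The cost is up to 14 more days of restriction for patients seen after Day 180. Scheduling Visit 7 on Days 166 to 180 avoids it. One small exposure remains: a patient released at Day 194 who returns later could still contribute a score under 8.3.1. The summary of out-of-window visits already planned there will show how often visits fall outside the window.

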3.9 Screen Failures

Screen failures are those subjects who have signed the informed consent, but are not eligible to start treatment following the Screening/Baseline assessments. A log of all subjects screened for the study but not entered into the study will be maintained by each investigational site. The reason(s) for screen failure will be recorded on the log.

3.10 Withdrawal Criteria

Potential reasons for discontinuation may include, but are not limited to:

Subject Withdrawal: Subject participation in a clinical trial is voluntary. The subject may discontinue participation (refuse all subsequent testing and follow-up procedures) at any time without penalty or loss of benefits.

Investigator Termination: The investigator may terminate the subject's participation without regard to the subject's consent if the investigator believes it is medically necessary and in the best interest of the subject.

Lost to Follow-up: The subject does not complete the 6 month follow-up but has not "officially" withdrawn from the study. Failure to return for follow-up visits is not a criterion for withdrawal. In order to consider a subject lost to follow-up, site personnel should make all reasonable efforts to locate and establish communication with the study subject. All attempts should be documented within the source documents, indicating date, time, method, and site personnel. A minimum of three documented attempts should be made without response from the study subject in order to classify a subject as lost to follow-up. Should subject discontinuation occur, the reason(s) for discontinuation must be documented in the source documents along with notification to Arthrex Inc. or designee. Subjects who withdraw or are discontinued from the study will not be replaced.

3.11 Study Duration

The study enrollment period will be approximately 12 months (365 days). The coprimary endpoints will be assessed at 6 months (180 days) posttreatment. Patients will continue to be followed out to 12 months (365 days) posttreatment until the last patient reaches the 6-month (180 days) time point. Therefore, the overall study duration will be approximately 24 months.

3.11 Unscheduled Visits

Unscheduled visits may occur due to changes in subject circumstances that require immediate attention. (e.g., adverse event: increased or uncontrolled pain requiring treatment).

3.12 Subject Compensation

Each subject who returns for each follow-up visit within the protocol required time frame will receive a reasonable compensation to offset the cost of meals, transportation, parking, and other such expenses, as approved by the IRB.

Compensation is provided to the subject by the investigational site. Compensation amounts are specified in the Informed Consent and the Clinical Trial Agreement.

4 Risk Analysis

4.1 Benefits

The Arthrex ACP system allows rapid and efficient concentration of platelets and growth factors from autologous blood for use at the treatment site. The unique double syringe allows for convenient and safe handling as the whole preparation process takes place in a closed system. The ACP system is more affordable, easier to use, and has quicker procedure time when compared to other conventional PRP devices. WBCs and RBCs are NOT concentrated within the ACP system. These cells can cause a detrimental effect on the healing process due to release of derivative proteins and reactive oxygen species.

If the procedure is successful, possible benefits may include significant decrease your knee pain, improvement in knee function and range of motion. It is not guaranteed that subject's condition will improve as a result of participating in this study and may receive no direct benefit at all.

4.2 **Risks and Mitigations**

Since ACP is autologous and prepared from a patient's own blood, there are no issues with transmission of diseases such as human immunodeficiency virus (HIV), hepatitis, or Creutzfeldt-Jacob disease (CJD or "mad cow" disease). Also, any immunogenic issues that could occur with allograft or xenograft preparations should not be a problem.^{23,38}

The potential risks associated with the ACP double syringe system can be split into two groups:

- Preclinical double syringe operation, and centrifugation
- Clinical delivery of ACP and the subsequent effects of ACP in the body

From the preclinical side, the primary concern is associated with the function and ease of use of the syringe, such as difficulty drawing blood through the syringe, or difficulty depressing the plunger. The risk to the patient, as a result of this is an additional needle stick. Arthrex has implemented appropriate manufacturing assembly steps, user training, and product testing procedures to ensure that the syringes meet customer requirements. Arthrex confirms that no other measures are necessary to mitigate risk.

From the clinical side, the procedure requires a peripheral blood draw as well as an IA injection. Potential risks to the patient can include: deep and superficial infections; allergies and other reactions; development of a hematoma; damage to blood vessels and nerve damage resulting in pain or numbness; and delayed wound healing. These risks can be mitigated by making sure that only trained personnel carry out all the blood draws and IA injections.

5 Device Description

5.1 Device Description

The Arthrex ACP® double syringe is a specially designed outer syringe which holds approximately 16 mL of liquid. The syringe is made of polypropylene, a well-known biocompatible material used for a wide variety of medical devices. Within this outer syringe, a smaller syringe is connected over a Luer-lock (hub) female connector. At the distal end of both syringes there is a male luer-lock connector (nozzle) for fitting the female connector (hub) or adaptor for connection to a syringe or cannula. A threaded screw cap (containing the Luer-lock nozzle) at the distal end of the outer syringe can be removed to allow the user to fill the outer syringe (Figure 5.1.1).

Figure 5.1.1

ACP double syringe with cap

The special design of the double syringe facilitates the rapid preparation of autologous PRP and concentrated PPP from a small sample of blood.

A Rotofix 32 A bench top centrifuge is used to centrifuge the double syringe (Figure 5.1.2). After centrifugation, the special design of the double syringe allows for the transfer of the supernatant (ACP) from the outer syringe into the smaller, inner syringe, under aseptic condition (Figure 5.1.3).

Figure 5.1.2

Rotofix 32 A bench top centrifuge

Figure 5.1.3

Supernatant (ACP) is aseptically transferred into the small, inner syringe

ACP Kit Series I – IDE-ABS-10011-IDE

Component #	Description	Qty
ABS-10014U	Double Syringe	1
REF-645	Double Syringe Luer Cap	1
REF-337	Tourniquet – Disposable, Latex-Free	1
REF-338	Alcohol Pads	1
REF-01530	Butterfly Needle Infusion Set, 19G	1
REF-340	Gauze Sponge, 2x2 in.	1
C12690-01	Band-Aid, Latex-Free	1
REF-443	Hypodermic Needle, 22G, 1.5"	1
	Patient Labels (inside kit)	2

5.2 Principle of Device Operation

The ACP® double syringe system is designed to facilitate the rapid preparation of autologous PRP from a small sample of blood. After centrifugation, the special design of the double syringe allows for

the transfer of the supernatant from the outer syringe into the inner, smaller syringe under aseptic condition.

A butterfly needle is used to withdraw approximately 16 mL of patient blood. The butterfly needle is removed and a screw cap is placed on the syringe. The double syringe is put into one bucket of the bench top centrifuge (Rotofix 32 A) for 5 min. at 1500 rpm.

Thereafter, the supernatant is transferred to the inner syringe under aseptic condition by pressing the wings of the double syringe together. See Figure 5.2.1 below for reference.

Figure 5.2.1 Principle of Operation

The ACP Kit contains the necessary components to facilitate blood draw

Withdraw blood using provided butterfly needle

Centrifuge 1500 rpm for 5 min

CONFIDENTIAL

PAGE 25 OF 98

Transfer plasma into smaller syringe and unscrew

ACP ready for use

5.3 Analytical Study

An analytical study was conducted to determine the amount of GFs, thrombocytes/platelets (T), erythrocytes/RBCs (E), and leukocytes/WBCs (L) present in ACP.

The density of the blood cells, triglycerides, and 7 selected GFs in ACP were compared to whole blood drawn from 12 healthy test subjects and centrifuged using the ACP double syringe System.

The GFs were determined on the basis of the whole blood samples and plasma samples using ELISA kits (R&D Systems, Inc.). A blood cell count was also performed (Bioscientia Labs, Germany).

Table 5.3.1 Analysis overview

Sample	Analysis
Whole blood	Ε, L, T
Whole blood plasma	GFs and triglycerides
ACP	Ε, L, T

Results:

The density of thrombocytes in the ACP was increased 2-fold compared to whole blood. The concentration of the leucocytes and erythrocytes in the ACP was 10% and 1% of the whole blood, respectively.

The concentration of all GFs in the ACP was significantly higher than in the whole blood.

The triglyceride values of the ACP do not differ from those for the whole blood.

See Table 5.3.2 for a complete list of the test results.

Table 5.3.2 Results of the ACP analysis

Cell Count		Whole Blood	ACP	
			(Autologous Conditioned Plasma)	
Thrombocytes (T)	Mean	242	550	
[10E3 / µl]	SD	62	126	
Erythrocytes (E)	Mean	4,97	0,05	
[10E6 / µl]	SD	0,24	0,01	
Leukocytes (L)	Mean	7,11	0,69	
[10E3 / µl]	SD	1,67	0,83	
Growth Factors		Whole Blood Plasma	ACP	
IGF-I	Mean	121	122	
[ng/ ml	SD	50	51	
EGF	Mean	113	396	
[pg/ ml]	SD	116	112	
VEGF	Mean	32	130	
[pg/ ml	SD	40	124	
PDGF-AB	Mean	2467	30979	
[pg/ ml]	SD	2210	8525	
PDGF-BB	Mean	1760	4529	
[pg/ ml]	SD	2042	1458	
TGF-b-1	Mean	36506	92824	
[pg/ ml]	SD	38380	21504	
TGF-b2	Mean	98	197	
[pg/ ml]	SD	128	131	
Triglyceride	Mean	506	466	
[mg/ ml]	SD	126	171	

6 Study Procedures

